4.3. Exploratory Objectives

The exploratory objectives may include evaluating the response to baricitinib treatment regimens on clinical measures and patient-reported outcomes (PROs).

These endpoints may include dichotomous endpoints or change from baseline for the following measures: IGA, Eczema Area and Severity Index (EASI), SCORing Atopic Dermatitis (SCORAD), Patient-Oriented Eczema Measure (POEM), Dermatology Life Quality Index (DLQI), Work Productivity and Activity Impairment (WPAI-AD), European Quality of Life–5 Dimensions–5 Levels (EQ-5D-5L), Itch Numeric Rating Scale (NRS), Atopic Dermatitis Sleep Scale (ADSS) Item 2 score, Skin Pain NRS, and Patient Global Impression of Severity (PGI-S-AD).

Additionally, assessment of background topical corticosteroids (TCS), such as the weight of sponsor-provided TCS and number of days not using TCS, will be analyzed. Patients continuing on placebo as responders will be assessed during the long-term extension for relevant efficacy endpoints.

Time to 4-point itch reduction during the first 14 days after initiation of treatment will be assessed.

Summary of IGA response (0,1) at Week 16 for the proportion of nonresponders with originating study treatment assignment in placebo, baricitinib 1 mg, or baricitinib 2 mg with IGA response (3,4) at the start of study JAHN (Week 0) will be provided.

For IGA (0,1), EASI75, and Itch NRS ≥ 4 -point improvement, a pooled response descriptive summary for baricitinib 2 mg to baricitinib 2 mg and baricitinib 4 mg to baricitinib 4 mg will be done for Week 0 through Week 52 based on I4V-MC-JAHL (JAHL)/I4V-MC-JAHM (JAHM), I4V-MC-JAIY (JAIY), and open label, respectively.

For all the randomized patients who have not entered into the substudy and received at least 1 dose in Period 2, the exploratory analyses will be assessed on the following endpoints: EASI change percent change from baseline, DLQI, SCORAD, POEM, Hospital Anxiety and Depression Scale (HADS). Open-label patients who were not entered into substudy and received at least 1 dose in Period 2 will be analyzed separately in a similar way.

In addition, for the Long-term Baricitinib 4-mg population, the following endpoints, IGA response (0,1), EASI, DLQI, SCORAD, and subjective characteristics of SCORAD (pruritus and sleep loss), will be analyzed in a descriptive way for Week 52 through 104 based on pooled patients, as well as by monotherapy and combination therapy study respectively.

For the final DBL, efficacy endpoints beyond Week 104 will be exploratory in nature and will be analyzed in a descriptive way using observed data, unless otherwise stated. For endpoint collected beyond Week 104, refer to protocol schedule of activities.

5. Study Design

5.1. Summary of Study Design

Study JAHN is a Phase 3, multicenter, double-blind study to evaluate the long-term safety and efficacy of daily baricitinib 1 mg, 2 mg, and 4 mg in patients with atopic dermatitis (AD) for approximately 2 years. The study will consist of 3 study periods and 1 substudy: randomized treatment withdrawal and downtitration. Patients entering Study JAHN will be classified as “responders,” “partial responders” or “nonresponders” based on the following criteria:

- **Responders (IGA of 0 or 1):** patients entering Study JAHN who have an IGA score of 0 or 1 and were not rescued in the originating study
- **Partial Responders (IGA of 2):** patients entering Study JAHN who have an IGA score of 2 and were not rescued in the originating study
- **Nonresponders:** any patient who does not meet the “responder” or “partial responder” definitions

Figure JAHN.5.1 illustrates the study design. The full visit schedule is outlined in the Study Schedule of Activities in the Protocol. Patients who completed originating studies, such as Studies JAHL, JAHM or JAIY may be eligible for enrollment into Study JAHN. This study also includes an open-label addendum for which patients do not have to complete an originating study.

[figure not shown]
Patients completing Studies JAHL, JAHM or JAIY will have had approximately 16 weeks of treatment with investigational product (IP) (baricitinib or placebo) and will enter Study JAHN at Visit 1; the final visit of Study JAHL, JAHM or JAIY will be the first visit of Study JAHN unless washout of a concomitant medication was required in which case a new Visit 1 is required. If oral systemic AD treatments were administered for rescue in the originating study, then a minimum washout of 4 weeks is required prior to study drug initiation in Study JAHN (Visit 1). Patients will have been using emollients daily in their originating study and thus will continue during Study JAHN participation.

Daily diary dispensation/collection will continue through the first 4 months of treatment in JAHN and then dispensation will resume at Week 48 for an additional 5 months of collection to capture PROs prior to and during the withdrawal and downtitration substudy (except for patients known not to be in the substudy).

Study JAHN will consist of 4 periods:

- **Screening and baseline period:** Screening should occur during the last visit of the originating study unless the patient received oral systemic AD treatment as rescue therapy during the originating study and needs additional time to complete the required 4-week washout period or the sponsor gave approval.
- **Treatment Period 1:** Treatment period from Week 0 to Week 52. Patients will be classified as responders, partial responders or nonresponders at the entry of Study JAHN based on the criteria given in Section 5.1.

- Treatment Period 2: Treatment period from Week 52 to 200 and will contain a randomized withdrawal and downtitration substudy. At Week 52, all patients will be evaluated for substudy eligibility, and the criteria are given in the Protocol. Patients not entered in the substudy will continue on their current treatment.
- Posttreatment follow-up period: Period from Week 200 (Visit 22) or Early Termination Visit (ETV) to approximately 28 days after the last dose of IP.

Abbreviations: BARI = baricitinib; IGA = Investigator’s Global Assessment; TCS = topical corticosteroids.

a Background TCS may be initiated or reinitiated at any time during the study, following the guidelines in the Protocol (Section 7.7.1) and will be provided as part of rescue or retreatment any time a patient’s IGA score becomes ≥ 3 as described in the Protocol (Sections 5.1.2.1 and 5.1.3.1).

b Eligible patients will be rerandomized in the withdrawal and downtitration substudy as described in the Protocol (Section 5.1.3.1). Patients who do not enroll in the substudy will remain on their treatment.

c Patients enrolled in the substudy will automatically be retreated if their IGA score becomes ≥ 3 as described in the Protocol (Section 5.1.3.1).

d Rescue is available as described in the Protocol (Section 5.1.2.1).

Figure JAHN.5.1. Illustration of study design for Clinical Protocol I4V-MC-JAHN.

5.2. Method of Assignment to Treatment

At entry into Study JAHN, patients who meet all criteria for enrollment will be randomized or assigned treatment by a computer-generated random sequence using an interactive web-response system (IWRS). Patients originally assigned to placebo, 1-mg baricitinib, or 2-mg baricitinib in Studies JAHL or JAHM, or patients originally assigned to placebo or 2-mg baricitinib in Study JAIY and classified as nonresponders, will be randomized in a 1:1 ratio to 2-mg baricitinib or 4-mg baricitinib and will be stratified by disease severity at baseline of JAHN (IGA 0, 1, 2 versus IGA 3 versus IGA 4). All other patients will be assigned to treatment in Study JAHN matching their prior assignment from Studies JAHL, JAHM, or JAIY.

Additional addendum patients will be permitted to enroll directly into Study JAHN on baricitinib 2 mg. These patients will not be blinded to treatment.

At Week 52, patients eligible for the withdrawal and downtitration substudy will be assigned to treatment by a computer-generated random sequence using an IWRS. Rerandomization will follow a 1:1:1 ratio allocation and will be stratified by disease severity (IGA 0, 1 versus IGA 2). Patients entering the substudy on baricitinib 4 mg will be rerandomized to baricitinib 4 mg, baricitinib 2 mg, and placebo; patients entering the substudy on baricitinib 2 mg will be rerandomized to baricitinib 2 mg, baricitinib 1 mg, and placebo.

The IWRS will be used to assign blister packs, each containing double-blind IP tablets, to each patient, starting at Visit 1 (Week 0), and at each visit up to and including Visit 21 (Week 184). Site personnel will confirm that they have located the correct blister packs by entering a confirmation number found on the blister packs into the IWRS.

This study will be conducted internationally in multiple sites. [Table JAHN.5.1](#) describes how regions were defined for stratification in the originating studies.

Table JAHN.5.1. Geographic Regions for Stratification

Region	Country
Europe	Austria, Czech Republic, Denmark, France, Germany, Hungary, Italy, Poland, Spain, Switzerland
Japan	Japan
Rest of World	Argentina, Australia, India, Israel, Korea, Mexico, Russia, Taiwan

6. A Priori Statistical Methods

6.1. Determination of Sample Size

It is anticipated that 95% of enrolled patients will complete Studies JAHL, JAHM, and JAIY and roll over into Study JAHN. Therefore, planned enrollment into Study JAHN from the originating Studies JAHL, JAHM, and JAIY will be approximately 1425 patients. Patients who are nonresponders at entry into Study JAHN and were not randomized to baricitinib 4 mg will be randomized 1:1 to either baricitinib 4 mg or baricitinib 2 mg and will be stratified by disease severity at baseline of JAHN (IGA 0, 1, and 2 versus IGA 3 versus IGA 4). This study is intended to evaluate patients' long-term response of baricitinib, and the sample sizes are not determined to detect differences between baricitinib and an appropriate comparator in a statistically powered manner. Additional patients may enroll from addenda or other studies.

Patients at Week 52 will be stratified by responder status (IGA 0 or 1 versus IGA 2) when entering the randomized withdrawal and downtitration substudy. It is estimated that there will be approximately 600 patients entering the randomized withdrawal and downtitration substudy. The substudy is meant to evaluate the change in clinical response after treatment withdrawal or downtitration and does not account for whether the sample size is sufficient to detect a difference between baricitinib and placebo. Maintenance of treatment benefit is defined as response of IGA 0, 1, or 2.

6.2. General Considerations

This plan describes *a priori* statistical analyses for efficacy, health outcomes, and safety that will be performed.

Statistical analysis of this study will be the responsibility of Eli Lilly and Company (Lilly). The statistical analyses will be performed using SAS® Version 9.4 or higher.

Not all displays described in this statistical analysis plan (SAP) will necessarily be included in the clinical study report (CSR). Not all displays will necessarily be created as a “static” display. Some may be incorporated into interactive display tools instead of or in addition to a static display. Any display described in this SAP and not included in the CSR would be available upon request.

Statistical tests of treatment effects and confidence intervals (CIs) will be performed at a 2-sided significance level of 0.05, unless otherwise stated.

Data collected at early termination visits will be mapped to the closest scheduled visit if it falls within the visit window as discussed in Section 6.2.2. For by-visit summaries, only visits in which a measure was scheduled to be collected will be summarized. Any unscheduled visit data will be included at the patient-level listings. However, the data will still be used in other analyses, including categorical analyses for safety.

6.2.1. Analysis Populations

Intent-to-treat (ITT) population: The ITT population analysis set is defined as all enrolled patients in Study JAHN.

Modified intent-to-treat (mITT) population: The mITT population analysis set is defined as all randomized patients who received at least one dose of the IP in Study JAHN.

The efficacy and health outcome analyses will be conducted on subsets of the mITT population, which is dependent on the objectives. For all analyses of patients from originating studies, responders, partial responders and nonresponders will be distinguished by their originating studies at entry of Study JAHN – monotherapy (JAHL/JAHM) and combination therapy (JAIY). Patients will be analyzed according to the treatment to which they were randomized.

The analysis of the primary objective will be conducted on the mITT population who are responders and partial responders (Section 5.1). Additionally, these endpoints will also be evaluated by parsing this group into responder mITT and partial responder mITT groups.

The populations for the secondary objectives (nonresponders who were on a baricitinib dose in originating study and nonresponders who were on placebo in originating study) will also be comprised of patients meeting the mITT definition. Exploratory objectives will also be conducted on the same populations.

For the database lock (DBL) that supports the United States (US) submission (13DEC2019) (subsequently referred to as the US DBL), the population originating from combination therapy study JAIY, Week 24 efficacy and health outcome analyses will be conducted on the **Week 24 efficacy evaluable set**. This subset of the mITT Population is anchored on the database cut-off date for the US DBL. Specifically, a patient will be included in the Week x efficacy evaluable set if their Week x visit has occurred or their expected Week x visit date plus a 15-day buffer is on or prior to the database cutoff date. The expected Week x visit date will be calculated as follows:
date of first dose date + (x weeks * 7 days) + 15 days.

For the US DBL, for Treatment Period 2 (downtitration and withdrawal), Week 56, Week 60, Week 64, and Week 68 efficacy analyses will be conducted on the Week 56, Week 60, Week 64, and Week 68 efficacy evaluable sets respectively. The efficacy evaluable sets are a subset of the mITT population and are anchored on the database cut-off date for the US DBL.

For the DBL in December 2021 and final DBL, the following analysis populations are defined for efficacy and health outcome analyses.

Randomized Downtitration Withdrawal Substudy Population: All patients (including open-label patients) who are rerandomized at Week 52, enter the substudy, and receive at least 1 dose of the IP in Period 2.

Re-Treatment Substudy Population: A subset of Randomized Downtitration Withdrawal Substudy Population who experience IGA ≥ 3 at any time in Period 2 and receive at least 1 dose of retreatment of the original dose.

Period 2 Nonsubstudy Population: All patients randomized at Week 0 of main Study JAHN (excluding open-label patients) who are not eligible to enter the substudy at Week 52 and receive at least 1 dose of the IP in Period 2.

Open-Label Period 2 Nonsubstudy Population: All patients enrolled in the open-label addendum who are not eligible to enter the substudy at Week 52 and receive at least 1 dose of the IP in Period 2.

Long-Term Baricitinib 4 mg Population: Patients initially randomized to baricitinib 4 mg in the originating studies and remain on 4-mg up to Week 52 of Study JAHN. At Week 52 of Study JAHN, patients also need to continue 4-mg and receive at least one dose in Period 2 regardless of eligibility of entering sub-study.

Safety population: For the purpose of Study JAHN alone, the safety population is defined as all patients who received at least 1 dose of IP in Study JAHN and who did not discontinue from the study for the reason ‘Lost to Follow-up’ at the first postbaseline visit in Study JAHN. For the safety analysis of Treatment Period 2, patients with at least 1 dose of IP in Treatment Period 2 will be included in the safety analysis of Treatment Period 2.

Safety analyses will be performed using the safety population and will be analyzed according to the following treatment groups (or cohorts) defined in [Table JAHN.6.1](#). Patients will be analyzed according to the dosing regimen to which they were assigned.

Table JAHN.6.1. Safety Population Treatment Groups

Treatment Groups for Treatment Period 1 (Week 0-52)	Definition
PBO	Placebo at entry to Study JAHN followed to end of Treatment Period 1 or censored at treatment change
BARI 1 mg	BARI 1 mg followed to end of Treatment Period 1 or censored at dose or treatment change
PBO/BARI 1 mg to BARI 2 mg	PBO/BARI 1 mg switching to BARI 2 mg at entry to Study JAHN followed to end of Treatment Period 1 or censored at dose or treatment change
BARI 2 mg	BARI 2 mg followed to end of Treatment Period 1 or censored at dose or treatment change
PBO/BARI 1 mg/BARI 2 mg to BARI 4 mg	PBO/BARI 1 mg/BARI 2 mg switching to BARI 4 mg at entry to Study JAHN followed to end of Treatment Period 1 or censored at dose or treatment change
BARI 4 mg	BARI 4 mg followed to end of Treatment Period 1 or censored at dose or treatment change
Pooled BARI	BARI 1 mg/BARI 2 mg/BARI 4 mg at entry to Study JAHN followed to end of Treatment Period 1 or censored at dose or treatment change
Treatment Groups for Treatment Period 2 (Week 52-200)	Definition
BARI 2 mg to PBO	Randomized to PBO in Treatment Period 2 (previously treated with BARI 2 mg) followed to end of study or censored at retreatment with BARI 2 mg

Treatment Groups for Treatment Period 2 (Week 52-200)	Definition
BARI 2 mg to BARI 1 mg	Randomized to BARI 1 mg in Treatment Period 2 (previously treated with BARI 2 mg) followed to end of study or censored at retreatment with BARI 2 mg
BARI 2 mg to BARI 2 mg	Randomized to stay on BARI 2 mg in Treatment Period 2 followed to end of study
BARI 4 mg to PBO	Randomized to PBO in Treatment Period 2 (previously treated with BARI 4 mg) followed to end of study or censored at retreatment with BARI 4 mg
BARI 4 mg to BARI 2 mg	Randomized to BARI 2 mg in Treatment Period 2 (previously treated with BARI 4 mg) followed to end of study or censored at retreatment with BARI 4 mg
BARI 4 mg to BARI 4 mg	Randomized to stay on BARI 4 mg in Treatment Period 2 followed to end of study
BARI 2 mg	Not part of the substudy, stayed on BARI 2 mg in Treatment Period 2 followed to end of study (this treatment group includes the open-label BARI 2 mg addendum patients)
BARI 4 mg	Not part of substudy, stayed on BARI 4 mg in Treatment Period 2 followed to end of study
Treatment Group for Treatment Periods 1 and 2 (Week 0-104) (for Box Plots Only)	Definition
PBO	Placebo at entry to Study JAHN followed to end of study or censored at treatment change
BARI 1 mg	BARI 1 mg followed to end of study or censored at dose or treatment change
BARI 2 mg to PBO	BARI 2 mg in Treatment Period 1, rerandomized to PBO in Treatment Period 2 followed to end of study or censored at retreatment with BARI 2 mg
BARI 2 mg to BARI 1 mg	BARI 2-mg in Treatment Period 1, rerandomized to BARI 1 mg in Treatment Period 2 followed to end of study or censored at retreatment with BARI 2 mg
BARI 2 mg to BARI 2 mg	BARI 2 mg in Treatment Period 1, rerandomized to stay on BARI 2 mg in Treatment Period 2 followed to end of study
BARI 4 mg to PBO	BARI 4 mg in Treatment Period 1, rerandomized to PBO in Treatment Period 2 followed to end of study or censored at retreatment with BARI 4 mg
BARI 4 mg to BARI 2 mg	BARI 4 mg in Treatment Period 1, rerandomized to BARI 2 mg in Treatment Period 2 followed to end of study or censored at retreatment with BARI 4 mg
BARI 4 mg to BARI 4 mg	BARI 4 mg in Treatment Period 1, rerandomized to stay on BARI 4 mg in Treatment Period 2 followed to end of study
BARI 2 mg	BARI 2 mg in Treatment Period 1, did not enter the substudy and stayed on BARI 2 mg in Treatment Period 2 followed to end of study (this treatment group includes the open label BARI 2 mg addendum patients)
BARI 4 mg	BARI 4 mg in Treatment Period 1, did not enter the substudy and stayed on BARI 4mg in Treatment Period 2 followed to end of study

Abbreviations: BARI = baricitinib; PBO = placebo.

An all-baricitinib exposure, defined as patients valid for the safety population with at least 1 dose of baricitinib anytime during Study JAHN, will be analyzed for the final analysis (final datalock).

Follow-up population: The follow-up population is defined as patients who entered the follow-up period and completed the follow-up visit.

For the February 2021 DBL, adverse event (AE) Period 1 tables will be summarized by treatment in Period 1, which include treatment group of (PBO, BARI 1-mg, BARI-2mg, BARI 4-mg, Pooled BARI).

For final DBL, AE tables will be summarized by treatment in Period 2 as specified in [Table JAHN.6.1](#).

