6.11. Efficacy Analyses

The general methods used to summarize efficacy data, including the definition of baseline value for assessments are described in Section 6.2.

Efficacy analyses will generally be analyzed according to the groups in Table JAHN.6.3 and patients will be analyzed according to the IP being analyzed in the objective.

Table JAHN.6.3. Efficacy Analyses: Comparisons or Treatment Paradigms

Treatment Period	Treatment Groups: Originating Study Treatment to JAHN Treatment	Comparison or Treatment Paradigms	Analysis
Treatment Period 1 (main JAHN protocol)	Responders and Partial Responders: PBO to PBO (PBO), BARI 1 mg to BARI 1 mg (BARI 1 mg), BARI 2 mg to BARI 2 mg (BARI 2 mg), BARI 4 mg to BARI 4 mg (BARI 4 mg)	PBO, BARI 1 mg, BARI 2 mg, BARI 4 mg; descriptive	Primary, Secondary, Exploratory
	Nonresponders: PBO to BARI 2 mg, PBO to BARI 4 mg, BARI 1 mg to BARI 2 mg, BARI 1 mg to BARI 4 mg, BARI 2 mg to BARI 2 mg, BARI 2 mg to BARI 4 mg, BARI 4 mg to BARI 4 mg	PBO to BARI 4 mg vs PBO to BARI 2 mg; BARI 1 mg to BARI 4 mg vs BARI 1 mg to BARI 2 mg; BARI 2 mg to BARI 4 mg vs BARI 2 mg to BARI 2 mg	Secondary, Exploratory
Treatment Period 2 (Randomized Withdrawal and Downtitration SubStudy)	Treatment Groups: Bari 4 mg at Week 52 Bari 4 mg to Bari 2 mg Bari 4 mg to PBO Bari 2 mg at Week 52	Bari 4 mg to Bari 2 mg Bari 4 mg to PBO	Secondary

Treatment Period	Treatment Groups: Originating Study Treatment to JAHN Treatment	Comparison or Treatment Paradigms	Analysis
	Bari 2 mg to Bari 1 mg Bari 2 mg to PBO	Bari 2 mg to Bari 1 mg Bari 2 mg to PBO	
Treatment Period 2 (Non substudy) (main JAHN population)	Treatment Groups: Bari 4 mg Bari 2 mg Bari 1 mg PBO	No comparison	Secondary, Exploratory
Treatment Period 2 (Non substudy) (open label Bari 2mg population)	Treatment Groups: Bari 2mg	No comparison	Secondary, Exploratory

Abbreviations: BARI = baricitinib; PBO = placebo.

[Table JAHN.6.4](#) includes the descriptions and derivations of the primary, secondary, and exploratory efficacy outcomes.

[Table JAHN.6.5](#) provides the detailed analyses including analysis type, method and imputation, population, time point, and comparisons for efficacy analyses.

Table JAHN.6.4. Description and Derivation of Primary, Secondary, and Exploratory Efficacy Outcomes

Measure	Description	Variable	Derivation / Comment	Imputation Approach if Missing Components

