European Quality of Life–5 Dimensions–5 Levels (EQ-5D-5L)	Observed values in 
 ▪ EQ-5D mobility ▪ EQ-5D self-care ▪ EQ-5D usual activities ▪ EQ-5D pain/ discomfort ▪ EQ-5D anxiety/ depression 	Descriptive statistics (Observed)	ITT	Weeks 0 to 24	Exploratory analysis
	Observed and Change from baseline in 
 ▪ EQ-5D VAS ▪ EQ-5D-5L UK Population-based index score ▪ EQ-5D-5L US Population-based index score 	Descriptive statistics (Observed)	ITT	Weeks 0 to 24	Exploratory analysis

Abbreviations: AD = atopic dermatitis; EE = efficacy evaluable; ITT = intent-to-treat; NRI = nonresponder imputation.

APP.1.2.14. Bioanalytical and Pharmacokinetic / Pharmacodynamic Methods

Pharmacokinetic, pharmacodynamic, and biomarker analyses will not be conducted.

APP.1.2.15. Safety Analyses

The safety data from this addendum will be pooled with the bari 2-mg treatment group from Study JAHN and will follow the same planned analyses given in Section 6.14. Refer to Section 6.14 for the planned analyses.

APP.1.2.15.1. Extent of Exposure

Refer to Section 6.14.1 for the planned analyses.

APP.1.2.15.2. Adverse Events

Refer to Section 6.14.2 for the planned analyses.

APP.1.2.15.2.1. Common Adverse Events

Not applicable.

APP.1.2.15.2.2. Serious Adverse Event Analyses

Refer to Section 6.14.2.2 for the planned analyses.

APP.1.2.15.2.3. Other Significant Adverse Events

Refer to Section 6.14.2.3 for the planned analyses.

APP.1.2.15.3. Clinical Laboratory Evaluation

Refer to Section 6.14.3 for the planned analyses.

APP.1.2.15.4. Vital Signs and Other Physical Findings

Refer to Section 6.14.3 for the planned analyses.

APP.1.2.15.5. Special Safety Topics, including Adverse Events of Special Interest

Refer to Section 6.14.5 for the planned analyses.

APP.1.2.16. Subgroup Analyses

Subgroup analyses will not be performed for Study JAHN(7.1).

APP.1.2.17. Protocol Deviations

Protocol deviations will be analyzed as described in Section 6.16 using the ITT population.

APP.1.2.18. Interim Analyses and Data Monitoring

Refer to Section 6.17 for the planned analyses.

APP.1.2.19. Planned Exploratory Analyses

The planned exploratory analyses are described in Section 6.18.

APP.1.2.20. Annual Report Analyses

Refer to Section 6.19.

APP.1.2.21. Clinical Trial Registry Analyses

Refer to Section 6.20.

APP.1.3. Unblinding Plan

Refer to Section 7.

APP.1.4. References

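### The Period 1 safety tables do not show the only randomised dose contrast: the randomised 4-mg arm is one row, but the randomised 2-mg arm is split and mixed with unrandomised patients

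*SAP*

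**What the plan says.** **Who is randomised.** SAP Section 5.2 states that patients from placebo, 1 mg or 2 mg (JAHL/JAHM), or from placebo or 2 mg (JAIY), who are "classified as nonresponders, will be randomized in a 1:1 ratio to 2-mg baricitinib or 4-mg baricitinib". The strata are IGA categories at JAHN baseline; prior dose is not a stratification factor. For the rest, "All other patients will be assigned to treatment in Study JAHN matching their prior assignment". Responders, partial responders and all 4-mg patients are therefore not randomised in Period 1.

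**Safety rows.** In Table JAHN.6.1 (Section 6.2.1) the 4-mg switch row is "PBO/BARI 1 mg/BARI 2 mg switching to BARI 4 mg at entry to Study JAHN followed to end of Treatment Period 1". The 2-mg switch row is "PBO/BARI 1 mg switching to BARI 2 mg at entry to Study JAHN followed to end of Treatment Period 1" and has no prior 2-mg patients. Those who stay on 2 mg are in a separate 2-mg row that makes no distinction by responder status. Appendix 1, APP.1.2.15, adds: "The safety data from this addendum will be pooled with the bari 2-mg treatment group from Study JAHN".

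**February 2021 lock.** Section 6.2.1 has the Period 1 adverse event tables summarised by treatment in Period 1, "which include treatment group of (PBO, BARI 1-mg, BARI-2mg, BARI 4-mg, Pooled BARI". No switch rows are listed.

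**Efficacy.** Table JAHN.6.3 and Section 6.2.3 pair the randomised nonresponders by prior dose, for example "BARI 2 mg to BARI 4 mg vs BARI 2 mg to BARI 2 mg".

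**Safety tests.** Section 6.2.3 names Fisher's exact test of each baricitinib dose against placebo. For continuous data the comparator is placebo or an appropriate one that is not identified. Sections 6.14.3 and 6.14.4 attach between-treatment p-values and Fisher tests to laboratory results and vital signs.

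**The concern.** The study is meant to evaluate long-term safety by dose. Nonresponders randomised to 2 mg or 4 mg give the one dose contrast in Period 1 that is protected by randomisation, and the safety rows do not show it.

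The comparator that the SAP does name is no substitute. Placebo nonresponders are all randomised to active drug, so the placebo row holds only placebo responders and partial responders. Section 6.2.3 expects few placebo responders. The tests therefore run against a small, unrandomised group.

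A reader who wants 4 mg against 2 mg will turn to the two switch rows or to the two dose rows. The switch rows differ in prior 2-mg exposure. That can matter because Section 6.14.2 takes the worst severity up to the first JAHN dose as baseline: an event that began on 2 mg in the originating study and persists unchanged is not treatment-emergent, whereas the same event in someone starting 2 mg at JAHN entry is. The dose rows differ in responder status and in the mix of unrandomised patients.

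**Working it through.** **1. Where each Period 1 group falls**

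| Group | Randomised at Week 0? | Table JAHN.6.1 row |
|---|---|---|
| a: placebo or 1-mg nonresponders to 2 mg | yes | 2-mg switch |
| b: 2-mg nonresponders to 2 mg | yes | 2 mg |
| r: 2-mg responders and partial responders | no | 2 mg |
| o: open-label addendum (about 250) | no | 2 mg |
| c: placebo or 1-mg nonresponders to 4 mg | yes | 4-mg switch |
| d: 2-mg nonresponders to 4 mg | yes | 4-mg switch |
| e: all patients continuing 4 mg | no | 4 mg |

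Placebo and 1-mg responders and partial responders stay in their own rows.

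**2. Can the arms be rebuilt from the rows?** The randomised 4-mg arm is c + d, which is the 4-mg switch row. The randomised 2-mg arm is a + b. The rows give a, and b + r + o. The pooled baricitinib row, whether or not it includes switchers and open-label patients, contains b only together with r. So b cannot be isolated, and a + b cannot be formed. The pairs by prior dose fail too: c and d appear only as a sum. A matrix-rank check over all rows gives the same answer.

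**3. Five-group layout, February 2021.** Read by Period 1 dose, the 2-mg group is a + b + r + o and the 4-mg group is c + d + e, so neither randomised arm is separable. Read as the rows of the same name, the 2-mg group is b + r + o, the 4-mg group is e, and the switchers have no dose group of their own. The contrast is missing either way.

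**4. Dilution of the 2-mg row (illustration).** Let N be the number randomised and f the share who came from 2 mg; then b is about f × N / 2. The documents give neither N nor f. Assume N of 600 to 1000, f of 0.25 to 0.50 and r of 50 to 200, with o = 250.
- Lowest: 0.25 × 600 / 2 = 75, and 75 / (75 + 250 + 200) = 14%.
- Highest: 0.50 × 1000 / 2 = 250, and 250 / (250 + 250 + 50) = 45%.

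**5. Comparing the two switch rows (illustration, no true dose effect).** The expected share of prior 2-mg patients is f in the 4-mg switch row and 0 in the 2-mg switch row. Assume equal numbers of nonresponders per originating arm and event proportions of 65% in new starters and 55% in those already exposed.
- JAHL/JAHM, 1-mg patients counted as new starters: (65 + 65 + 55) / 3 = 61.7% against 65%, difference -3.3 points.
- JAHL/JAHM, 1-mg patients counted as already exposed: (65 + 55 + 55) / 3 = 58.3% against (65 + 55) / 2 = 60%, difference -1.7 points.
- JAIY (placebo and 2 mg only): (65 + 55) / 2 = 60% against 65%, difference -5 points.

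If only prior 2 mg counts, the difference is f × (risk with prior 2 mg minus risk without). With f from 0.20 to 0.50 and a risk 5 to 15 points lower after prior 2 mg (all assumed), it runs from 0.20 × (-5) = -1.0 to 0.50 × (-15) = -7.5 points. Table JAHN.6.1 does not split by originating study, so the separate JAHL/JAHM and JAIY figures correspond to no planned row. None of these figures describes the five-group tables.

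**6. With the randomised arms as columns.** The prior 2-mg share is f in both, in expectation, and the spurious difference from prior exposure is 0.

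**The case against.** The strongest reply is that the rows are exposure cohorts: unchanged, switched to 2 mg, switched to 4 mg. A patient who goes from 2 mg to 2 mg has not switched, so the layout is coherent for its purpose. Pooling the open-label patients is declared and serves the addendum's aim of enlarging the 2-mg safety database. Section 6.14 also sends detailed safety work to integrated analyses that are not among these documents, and sample sizes were not set to detect differences. All of this stands, and it is a reason to keep the cohort rows. It does not supply the missing contrast: Section 6.14 still plans JAHN-alone safety tables on these groups, and whether the integrated plans restore it cannot be seen.

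Three stronger readings are tempting, and the documents support none of them.
- *A biased 4-mg against 2-mg safety test is planned.* No section plans a test of the 4-mg switch row against the 2-mg switch row.
- *The randomised comparison is lost.* It is absent only from the planned rows; patient-level data identify both arms.
- *The layout makes 4 mg look safer by a known amount.* The event proportions, the arm sizes and hence the direction are assumed. The JAHL/JAHM figure halves once 1-mg patients count as already exposed.

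**Conclusion.** The point holds as a gap in tabulation. From the group definitions alone, the randomised 2-mg arm cannot be recovered from the seven Period 1 rows, and neither randomised arm can be recovered from the five February 2021 groups. Period 1 safety is thus shown without its only randomised dose contrast, although efficacy keeps that contrast. This conclusion needs no numerical assumption.

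The consequence for a reader who compares the nearest rows is confounding by prior exposure (seven rows) or by responder status and unrandomised patients (five groups read by dose). Its size and direction are not established. About -1.7 to -3.3 points for JAHL/JAHM is an illustration that rests on equal nonresponder numbers per arm, proportions of 65% and 55%, and no dose effect. The change is worth making because it removes this source of bias at almost no cost.

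**What to change.** Keep the exposure-cohort rows of Table JAHN.6.1. Add one supplementary Period 1 safety table limited to nonresponders randomised at Week 0, with two columns: randomised to 2 mg and randomised to 4 mg, each from placebo, 1 mg or 2 mg.

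- **Content:** adverse event overview, treatment-emergent events, serious events, and events leading to permanent discontinuation of study drug.
- **Statistics:** counts, percentages, and the risk difference (4 mg minus 2 mg) with 95% CI. The Newcombe-Wilson interval already specified in Section 6.2.3 would serve.
- **Exclusions:** open-label patients, responders, partial responders and patients continuing 4 mg.
- **Label:** supplementary and descriptive. SAP Version 8 records that data up to Week 104 are already locked, so a new formal test would be post hoc, and none is needed.

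The cost is one extra table and a short SAP paragraph. It uses existing data, with no new patients or visits.
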